8.1.1.1 Definition of an adverse event

An adverse event is defined as any untoward medical occurrence or experience in a patient or clinical investigation subject which occurs following the application of the study treatment regardless of the causal relationship. Examples of adverse events include but are not limited to:

- Abnormal test findings;
- Clinically significant symptoms and signs;
- Changes in physical examination findings;
- ...

A serious adverse event is defined as any undesirable experience occurring to a patient, whether or not considered related to the protocol treatment. Worsening of signs and symptoms should be reported as adverse events in the appropriate section of the eCRF. Disease progression should not be reported as adverse event.

Abnormal Test Findings

The criteria for determining whether an abnormal objective test finding should be reported as an adverse event are as follows:

- Test result is associated with accompanying symptoms, and/or
- Test result requires additional diagnostic testing or medical/surgical intervention, and/or
- Test result leads to discontinuation from the trial, significant additional therapy, and/or
- Test result is considered to be an adverse event by the investigator or sponsor.

Merely repeating an abnormal test, in the absence of any of the above conditions, does not constitute an adverse event. Any abnormal test result that is determined to be an error does not require reporting as an adverse event.

Serious Adverse Events

A serious adverse event is any untoward medical occurrence that:

- Results in death;
- Is life-threatening (immediate risk of death);
- Requires inpatient hospitalization or prolongation of existing hospitalization;
- Results in persistent or significant disability/incapacity;
- Is an important medical event. Medical and scientific judgment should be exercised in determining whether an event is an important medical event. An important medical event may not be immediately life-threatening and/or result in death or hospitalization. However, if it is determined that the event may jeopardize the patient and may require intervention to prevent one of the other outcomes listed in the definition above, the important medical event should be reported as serious. An example of such events is intensive treatment in an emergency room or at home for convulsions that do not result in hospitalization.

Progression of the pathology during the study (including signs and symptoms of progression) should not be reported as an adverse event unless the outcome is fatal during the trial or within the safety reporting period. Hospitalizations due to signs and symptoms of disease progression should not be reported as serious adverse events. If the pathology has a fatal outcome during the trial or within the safety reporting period, then the event leading to death must be recorded as a serious adverse event.

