- Adverse Events – Adverse events that are recorded in this trial are medical or surgical complications. Nature of the complication, date of appearance, relationship to the surgical procedure/trial intervention, offered treatment and outcome will be recorded. Patients will be followed for adverse events during the study until at least the first follow-up appointment, or until all serious adverse events have resolved or are determined to be “chronic” or “stable”, whichever is later. Serious adverse events should be monitored and reported from the time that the patient is included in the study (cfr. Part 8).
- Concomitant therapy – concomitant medications and treatments will be recorded from the time that the patient is included, during the study, and up until the first follow-up appointment.
- CT-scan – CT imaging of the brain:
 - Signs of increased intracranial pressure of any cause (e.g. trauma, anoxia, ...), requiring placement of an EVD (e.g. GCS \leq 8)
 - Hematoma volume and evolution, evolution of midline shift
- Survival status – information on the patient’s post-operative survival will be collected for all patients until the first follow-up appointment.

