8.1.1.2 Hospitalization

Adverse events reported from clinical trials associated with hospitalization or prolongation of hospitalization are considered serious. Any initial admission (even if less than 24 hours) to a healthcare facility meets these criteria. Admission also includes transfer within the hospital to an acute/ICU (e.g. from the psychiatric wing to a medical floor, medical floor to a coronary care unit, neurological floor to a tuberculosis unit).

Hospitalization does not include the following:

- Rehabilitation facilities;
- Hospice facilities;
- Respite care (e.g. caregiver relief);
- Skilled nursing facilities;
- Nursing homes;
- Routine emergency room admissions.

For same-day surgeries (outpatient/ambulatory procedures), hospitalization or prolongation of hospitalization in the absence of a precipitating, clinical adverse event is not in itself a serious adverse event. Examples include:

- Admission for treatment of a pre-existing condition not associated with the development of a new adverse event or with a worsening of the pre-existing condition (e.g. for work-up of persistent pre-treatment lab abnormality, for single treatment-responsive seizure in a patient with known epilepsy);
- Social admission (e.g. patient has no place to sleep);

- Administrative admission (e.g. for yearly physical exam);
- Protocol-specified admission during a clinical trial (e.g. for a procedure required by the trial protocol);
- Optional admission not associated with a precipitating clinical adverse event (e.g. for elective cosmetic surgery);
- Pre-planned treatments or surgical procedures should be noted in the baseline documentation for the entire protocol and/or for the individual patient;
- Admission exclusively for the administration of blood products;
- Diagnostic and therapeutic non-invasive and invasive procedures, such as surgery, should not be reported as adverse events. However, the medical condition for which the procedure was performed should be reported if it meets the definition of an adverse event. For example, an acute appendicitis that begins during the adverse event reporting period should be reported as the adverse event, and the resulting appendectomy should be recorded as treatment of the adverse event.

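### Section 8.1.1.1 both requires and excludes reporting of non-fatal worsening and leaves progression undefined, so drain-related deterioration may be omitted from adverse event counts

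*Combined protocol and SAP*

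**What the plan says.** Section 8.1.1.1 contains these rules:

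- "Worsening of signs and symptoms should be reported as adverse events in the appropriate section of the eCRF".
- The very next sentence: "Disease progression should not be reported as adverse event".
- At the end of the section, the exclusion is widened: "Progression of the pathology during the study (including signs and symptoms of progression) should not be reported as an adverse event". The only exception is a fatal outcome; such a case is then recorded as a serious adverse event.
- Admissions are covered as well: "Hospitalizations due to signs and symptoms of disease progression should not be reported as serious adverse events".

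The protocol does not define progression. It gives no rule, and describes no adjudication, for separating progression from failure of the drain or harm from the procedure.

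Other provisions bear on the same events. Section 4.2 states "Adverse events that are recorded in this trial are medical or surgical complications", with their relationship to the procedure. Section 8.1.1.1 makes an abnormal finding reportable on several grounds, one of which is "Test result requires additional diagnostic testing or medical/surgical intervention, and/or". Section 8.1.1.2 says of repeat procedures that "the medical condition for which the procedure was performed should be reported if it meets the definition of an adverse event". Sections 8.1.1 and 8.1.1.1 call for adverse events to be captured whatever their suspected cause.

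**The concern.** The enrolled patients have raised intracranial pressure or bleeding. A drain that is blocked or off target, or that has caused a haemorrhage, can produce the same picture: a falling clinical score, a growing haematoma, a larger midline shift. An investigator who sees this has one sentence telling them to report it and another telling them not to, and the choice turns on presumed cause.

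That choice matters because the safeguards operate on events already recorded as adverse events. Section 8.1.3 treats unknown causality as related to the product. Section 8.1.2 requires a Clavien-Dindo grade, section 8.2 immediate notification of serious events, and section 8.1 semi-annual frequencies. An event labelled progression can bypass all four. Section 8.1.1 also states in advance that the device is not expected to cause any adverse event, and in a single-arm study the investigators know that it was used.

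At stake are the completeness of safety reporting during the trial and the complication rate, a secondary endpoint that is to be compared with standard practice.

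**Working it through.** The plan states no figure for this rule, so there is none to reproduce. The check has two parts.

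**1. One event followed through the rules.** Take a non-fatal neurological deterioration some days after placement, with uncertain cause.

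- Worsening rule (8.1.1.1): reportable.
- Progression rule (8.1.1.1): not reportable if judged a sign of the disease.
- Seriousness: section 8.1.1.2 counts transfer within the hospital to intensive care as an admission, hence serious. The hospitalisation exclusion in 8.1.1.1 removes the same transfer if it is attributed to progression.
- Abnormal-test rule (8.1.1.1): reportable if the finding comes with symptoms or leads to further testing or intervention. Nothing says whether this overrides the progression rule when the finding is itself a sign of progression.
- Repeat-procedure rule (8.1.1.2): reportable only if the condition meets the adverse event definition, which returns to the question at issue.
- CT within 24 hours (4.1.3): shows drain position in every patient. Later in-hospital CT is done only when clinically needed (Table 4), so later blockage or bleeding has no scheduled in-hospital image.

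The outcome depends on the label. The exposure is greatest for clinical worsening without a test finding or an intervention.

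**2. Scale.** Inputs: n = 10 to 15 (section 5.2), and a historical overall complication rate p of 14.2% to 16.1%, which covers infection, bleeding after placement and malposition (section 1.3).

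Expected events, n × p:

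- n = 10: 10 × 0.142 = 1.42; 10 × 0.161 = 1.61
- n = 15: 15 × 0.142 = 2.13; 15 × 0.161 = 2.415

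Probability of at least one event, 1 − (1 − p)^n:

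- n = 10: 1 − 0.858^10 = 0.78; 1 − 0.839^10 = 0.83
- n = 15: 1 − 0.858^15 = 0.90; 1 − 0.839^15 = 0.93

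Effect of one event recoded as progression, 100/n:

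- n = 10: 10.0 percentage points
- n = 15: 6.7 percentage points

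As a share of the expected count, one event is between 1/2.415 = 41% and 1/1.42 = 70%.

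**The case against.** The strongest reply is that the protocol already treats drain problems as complications. Section 4.2 records medical and surgical complications. Clavien-Dindo grade I in section 8.1.2 covers any deviation from the usual postoperative course, grade III covers reintervention, and the grade IV footnote names brain haemorrhage. A CT showing a misplaced drain in a worsening patient meets the abnormal-test criteria. The progression rule itself does not mention drain failure. The two adjacent sentences in 8.1.1.1 can also be read as a rule and its exception.

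Most of this stands, and it rules out several stronger readings:

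- *Drain failure is recorded only if fatal, or is lost.* A reader might infer this from the exclusion, but the routes above remain open. The Kakarla grade, number of passes, clinical scales, revision rate, rate of fall in intracranial pressure and midline shift are also collected outside adverse event reporting.
- *The 7-13% poor-placement rate could be reported as zero.* That figure is the worst Kakarla grade, read on CT for the primary endpoint. Adverse event coding cannot change it, and the documents do not link it to a rate of clinical deterioration.
- *Comparisons with history are biased in favour of augmented reality.* The direction cannot be shown, because the documents do not say how historical events were counted. If the institutional review also left out progression, the omission need not be differential.

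The reply does not close the gap. Read as rule and exception, the text still has an exception without a boundary. The endpoints listed do not trigger notification of a serious event. Section 9.1 provides for an independent committee to review results but describes no adjudication of progression.

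**Conclusion.** The conflict is real, and it is confined to non-fatal worsening. A written rule lets presumed cause decide whether such an event enters the safety counts, and the term that decides it is undefined. The consequence is possible misclassification in adverse event and serious adverse event reporting; it is not disappearance from the trial's data.

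One recoded event would move the observed complication rate by 6.7 to 10 points, when 1.4 to 2.4 events are expected. This rests on two assumptions: that the historical rate applies to these patients, and that the complication rate is drawn from adverse event records, which section 5.1 does not state. How often recoding would happen cannot be estimated from the documents.

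This is a cheap improvement to the wording. It does not undermine the primary endpoint.

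**What to change.** Reconcile the statements in section 8.1.1.1 with each other and with sections 4.2 and 8.1.1.2:

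1. Record as an adverse event any neurological worsening after drain placement, and any CT finding that meets the existing abnormal-test criteria in 8.1.1.1. Making every new CT finding an adverse event would go beyond those criteria and is not needed.
2. Assess each such event for seriousness against the existing list and for causality under 8.1.3.
3. Define progression, and keep it only as an attribution field on the form.
4. State that the progression exclusions, including the one for hospitalisations, do not apply to worsening for which a drain- or procedure-related cause has not been excluded.

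The cost is a protocol wording change and a few more forms in 10-15 patients. The downside is that some recorded events will prove to be the natural course of the disease; the attribution field lets these be shown separately.

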8.1.1.2 Hospitalization

Adverse events reported from clinical trials associated with hospitalization or prolongation of hospitalization are considered serious. Any initial admission (even if less than 24 hours) to a healthcare facility meets these criteria. Admission also includes transfer within the hospital to an acute/ICU (e.g. from the psychiatric wing to a medical floor, medical floor to a coronary care unit, neurological floor to a tuberculosis unit).

Hospitalization does not include the following:

- Rehabilitation facilities;
- Hospice facilities;
- Respite care (e.g. caregiver relief);
- Skilled nursing facilities;
- Nursing homes;
- Routine emergency room admissions.

For same-day surgeries (outpatient/ambulatory procedures), hospitalization or prolongation of hospitalization in the absence of a precipitating, clinical adverse event is not in itself a serious adverse event. Examples include:

- Admission for treatment of a pre-existing condition not associated with the development of a new adverse event or with a worsening of the pre-existing condition (e.g. for work-up of persistent pre-treatment lab abnormality, for single treatment-responsive seizure in a patient with known epilepsy);
- Social admission (e.g. patient has no place to sleep);

- Administrative admission (e.g. for yearly physical exam);
- Protocol-specified admission during a clinical trial (e.g. for a procedure required by the trial protocol);
- Optional admission not associated with a precipitating clinical adverse event (e.g. for elective cosmetic surgery);
- Pre-planned treatments or surgical procedures should be noted in the baseline documentation for the entire protocol and/or for the individual patient;
- Admission exclusively for the administration of blood products;
- Diagnostic and therapeutic non-invasive and invasive procedures, such as surgery, should not be reported as adverse events. However, the medical condition for which the procedure was performed should be reported if it meets the definition of an adverse event. For example, an acute appendicitis that begins during the adverse event reporting period should be reported as the adverse event, and the resulting appendectomy should be recorded as treatment of the adverse event.

8.1.2 Severity Assessment

Complications will be classified as medical (infection, electrolyte disturbance, etc.) or surgical. The investigator will use the following definitions of severity as defined by the Clavien-Dindo classification [45] to describe the maximum intensity of the adverse event (*Table 5*). The grade reported in the adverse event eCRF must be consistent with the description of the Clavien-Dindo grade included in the narrative section of the serious adverse event report.

Table 5. Classification of Postoperative Complications (Clavien-Dindo)

Grade	Definition
Grade I	Any deviation from the normal postoperative course without the need for pharmacological treatment or surgical, endoscopic and radiological interventions. Allowed therapeutic regimens are: drugs as antiemetics, antipyretics, analgesics, diuretics, electrolytes, and physiotherapy. This grade also includes wound infections opened at the bedside.
Grade II	Requiring pharmacological treatment with drugs other than such allowed for grade I complications. Blood transfusions and total parenteral nutrition are also included.
Grade III	Requiring surgical, endoscopic or radiological intervention
Grade IIIa	Intervention not under general anesthesia
Grade IIIb	Intervention under general anesthesia
Grade IV	Life-threatening complication (including CNS complications)* requiring IC/ICU-management
Grade IVa	single organ dysfunction (including dialysis)
Grade IVb	multorgan dysfunction
Grade V	Death of a patient
Suffix "d"	If the patient suffers from a complication at the time of discharge, the suffix "d" (for "disability") is added to the respective grade of complication. This label indicates the need for a follow-up to fully evaluate the complication.

*Brain hemorrhage, ischemic stroke, subarachnoid hemorrhage, but excluding transient ischemic attacks.

CNS, central nervous system; IC, intermediate care; ICU, intensive care unit

Table 5. Classification of Postoperative Complications (Clavien-Dindo)

Note the distinction between the severity and the seriousness of an adverse event. A severe event is not necessarily a serious event. For example, a headache may be severe (interferes significantly with subject's usual function) but would not be classified as serious unless it met one of the criteria for serious adverse events, listed above.

8.1.3 Causality Assessment

The investigator's assessment of causality must be provided for all adverse events (serious and non-serious). An investigator's causality assessment is the determination of whether there exists a reasonable possibility that the investigational product caused or contributed to an adverse event. If the investigator's final determination of causality is unknown and the investigator does not know whether or not investigational product caused the event, then the event will be handled as "related to investigational product" for reporting purposes. If the investigator's causality assessment is "unknown but not related to investigational product", this should be clearly documented on trial records. In addition, if the investigator determines a serious adverse event is associated with trial procedures, the investigator must record this causal relationship in the source documents and eCRF, as appropriate, and report such an assessment in accordance with the serious adverse event reporting requirements, if applicable.

8.1.4 Withdrawal due to adverse events

Withdrawal due to adverse events should be distinguished from withdrawal due to insufficient treatment results, according to the definition of adverse event noted earlier, and recorded on the appropriate adverse event eCRF page. When a patient withdraws due to a serious adverse event, the serious adverse event must be reported in accordance with the reporting requirements defined below.

8.2 Reporting period

Serious adverse events require immediate notification beginning from the time that the patient is included in the study, through and including the first follow-up appointment. Any serious adverse event occurring any time after the reporting period must be promptly reported if a causal relationship to the investigational product is suspected. Adverse events (serious and non-serious) should be recorded on the eCRF from the time the patient is included in the study until the first follow-up appointment. Death must be reported if it occurs during the serious adverse event reporting period, irrespective of any intervening treatment.

8.2.1 Reporting Requirements

The investigator is to report all directly observed adverse events and all adverse events spontaneously reported by the trial patient. In addition, each trial patient will be questioned about adverse events.

Each adverse event is to be assessed to determine if it meets the criteria for serious adverse event. If a serious adverse event occurs, expedited reporting will follow local and international regulations, as appropriate. Adverse event reporting to regulatory authorities will be carried out in accordance with applicable Belgian regulations.

All adverse events will be reported on the adverse event page(s) of the eCRF. It should be noted that the form for collection of serious adverse event information is not the same as the adverse event eCRF. Where the same data are collected, the forms must be completed in a consistent manner. For example, the same adverse event term should be used on both forms. Adverse events should be reported using concise medical terminology on the eCRFs as well as on the form for collection of serious adverse event information.

9 Quality assurance

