Secondary objectives/endpoints	
 • Improvement of user experience (intuitiveness, ergonomics, quickness; using the questionnaires in Appendix B) • Decrease of duration of procedure compared to same procedure performed without AR (based on historical values of procedure time, recorded at our institution) • Decrease of difference in outcome (accuracy scale) and of difference in duration of procedure between surgeons of different expertise levels compared to same intervention without AR (flattening of the learning curve) • Improvement of clinical outcome measures with AR-assisted surgery compared to standard practice (using the scales in Appendix C) • Improvement of pathology-specific clinical outcome measures: 
 ◦ Revision rate ◦ Complication rate ◦ Velocity of the decrease in ICP ◦ Evolution of midline shift

Exploratory objectives/endpoints	
 Explore development and optimization of an efficient and ergonomic workflow in a well-structured pipeline (pipeline from imaging to display of holograms) Explore and describe necessity for continuous implementation of technical advances improving the AR experience, such as: 
 Correcting for inattentional blindness (confusion between real and virtual world), Correcting for the use of historical images (i.e. updating preoperative images to better reflect the current situation), Implementing marker-free navigational tracking, Exploring cooperation by offering different points-of-view for multiple surgeons, Explore assistance of these interventions by using telepresence, ...
Safety monitoring	
All data from every single patient will be collected in a unique electronic Case Report Form (eCRF) which perfectly matches the source documents (e.g. study charts at the hospital). It is the investigator's responsibility to ensure completion and to review and approve all eCRF data. Thus, accuracy and authenticity of all data entered on the eCRFs is guaranteed by the investigator. Adverse events, both related and unrelated to study treatment, will be monitored on an ongoing basis and their frequencies reported semi-annually. Clinical outcome data will be tabulated and compared to historical values from literature as well as normal ranges for the institution, based on retrospective review of historical clinical data from the institution.

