4.1.3 Post-operative phase & follow-up

Within 24h after surgery the patient will undergo a CT-scan to assess the position of the newly-placed drain. The primary endpoint, accuracy of drain placement evaluated on the immediate postoperative CT and graded according to clinical relevance, will be evaluated using the abovementioned Kakarla scale (*Table 2-1*).

In the further post-operative period, the patient's status will be monitored as it would be for every patient undergoing standard treatment for the abovementioned pathologies: in the immediate post-operative phase the patient is monitored in the Intensive Care Unit (ICU). In the following days the patient may undergo additional imaging of the brain if deemed necessary, and his/her clinical status will be continuously monitored, as is common practice. Based on the clinical evolution, the drain may or may not be removed, and the patient may or may not be transferred to the neurosurgical ward.

As soon as the patient is deemed adequately fit, he/she will be discharged from the hospital and a first follow-up appointment will be planned after 6 weeks. At this appointment the patient's clinical status and cranial imaging status will be assessed one final time, after which the patient has completed his/her participation in the trial.

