4.2 Clinical evaluation, imaging & follow-up

Patients will be clinically monitored in accordance with standard of care for patients requiring EVD placement. We do not intend to do extensive research concerning the pathology, but rather want to get a notion of the possible difference in outcome related to the use of the HoloLens. The evaluations mentioned in this chapter will therefore be limited to the regular standard of care and only data obtained until the first follow-up appointment will be used for the trial. The schedule and types of assessments are presented in *Table 4*. The schedule is flexible as long as changes do not, in the opinion of the investigator, expose the patient to undue risk or induce bias in the evaluation of the endpoints. Data from the specified assessments will be collected in the **electronic Case Report Form (eCRF)**.

Protocol related procedures and assessments	Screening	Surgery	Post-operative period	Hospital discharge	Follow-up
	≤ Day 0	Day 0	Weekly		
Signed IC	X				
Prior medical history	X				
Physical examination	X	X	X	X	X
Clinical follow-up scales	X	X	X	X	X
Adverse events monitoring	X ↳			X	X
Concomitant therapy	X ↳			X	X
Other assessments					
CT-scan	X	X within 24h following surgery	(X) when deemed necessary for clinical reasons		X
Study treatment					
Surgery using HoloLens		X			
Survival status					X

Table 4. Protocol related procedures and assessments. The bold line indicates the end of the patient's participation in the trial.

Assessments outlined in *Table 4* include the following components:

- Prior medical history – diagnosis, prior and/or current treatments, history of other diseases (active or resolved), concomitant illnesses, and demographics.

- Physical examination – examination of major body systems (especially neurological evaluation), body weight and height (at screen only), vital parameters (i.e. temperature, blood pressure, and heart rate) and clinical follow-up scores (GCS, mRS, NIHSS, MGS; Appendix C).

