8.1 Safety Monitoring

Adverse events will be monitored on an ongoing basis and their frequencies reported semi-annually. The worst event for each patient will be described. Both events related and unrelated to treatment will be captured. Clinical outcome data will be tabulated and compared to normal ranges for the institution, based on historical values obtained at the institution.

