8.1.1 Adverse events

All observed or volunteered adverse events regardless of suspected causal relationship to the investigational product(s) or intervention will be reported as described in the following sections. For all adverse events, the investigator must pursue and obtain information adequate both to determine the outcome of the adverse event and to assess whether it meets the criteria for classification as a serious adverse event (cfr. below) requiring immediate notification to the study sponsor / IRB / **Internal Ethics Committee** (IEC). For all adverse events, sufficient information should be obtained by the investigator to determine the causality of the adverse event. The investigator is required to assess causality. For adverse events with a causal relationship to the investigational product, follow-up by the investigator is required until the event or its sequelae resolve or stabilize at a level acceptable to the investigator.

As the use of the HoloLens has no direct impact on the workflow of the standard surgical procedure, we do not expect it to cause any adverse events whatsoever. We expect general surgery-related complications as they would happen in the standard of care for the abovementioned pathologies, but none of these complications are directly linked to the use of the device.

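### Complications are collected differently in AR patients and in the institutional historical controls, so the complication-rate comparison is not like for like; the net direction of bias cannot be determined

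*Combined protocol and SAP*

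**What the plan says.** Section 5.1 lists complication rate among the pathology-specific secondary endpoints and words the group as an improvement.

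For AR patients, section 8.1.1 says "All observed or volunteered adverse events regardless of suspected causal relationship to the investigational product(s) or intervention will be reported". Section 8.2 says that serious and non-serious events "should be recorded on the eCRF from the time the patient is included in the study until the first follow-up appointment", a visit that section 4.1.3 plans 6 weeks after discharge. Section 8.2.1 adds that "each trial patient will be questioned about adverse events". Section 4.2 links these records to the endpoint: "Adverse events that are recorded in this trial are medical or surgical complications". Section 8.1.2 grades them by Clavien-Dindo, which starts at any deviation from a normal postoperative course.

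For the comparator, section 8.1 says that clinical outcome data will be "compared to normal ranges for the institution, based on historical values obtained at the institution". The safety monitoring row of the synopsis says these ranges are "based on retrospective review of historical clinical data from the institution", and names literature values as a second comparator.

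Section 5.4 describes matching, cut-offs and one-sided Fisher's exact tests for Kakarla accuracy only. It says nothing about how complications are to be compared.

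**The concern.** A complication rate depends on how events are looked for as well as on how often they happen. AR patients are asked about events and have dedicated adverse event pages. Historical patients were treated before this protocol, so they had neither, and a later reviewer finds only what was charted at the time. With the same true risk, the two methods can give different observed rates.

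At stake is the reading of one secondary endpoint. A difference, or the absence of one, between the AR rate and the institutional rate could reflect collection rather than the system. Section 5.2 says positive results may lead to a larger randomised trial, so even a descriptive comparison may carry weight.

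**Working it through.** **1. The plan's own figures.** The plan gives no sample size, test or expected difference for complications. The 67 in section 5.2 concerns accuracy. It reproduces as a per-group number (one-sided Fisher test, 80% against 95%, alpha 0.05: 67 per group gives 80.6% power) and has no bearing here.

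**2. The two sources side by side.**

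| Feature | AR patients | Institutional controls |
|---|---|---|
| Timing | Prospective (8.2) | Retrospective (synopsis) |
| Patients asked about events | Yes (8.2.1) | Not under this protocol |
| Event scope | All events, serious or not, any causality (8.1.1, 8.2) | Not stated |
| Time window | Inclusion to first follow-up (8.2) | Not stated |
| Common definition or form | None given | None given |

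Scheduled examinations are not a shown difference. Section 4.2 says "The evaluations mentioned in this chapter will therefore be limited to the regular standard of care", and section 5 says follow-up does not differ from the standard. The schedule in 4.2 also contains the CT described in 4.1.3 ("Within 24h after surgery the patient will undergo a CT-scan to assess the position of the newly-placed drain"), so the documents present that scan as usual care. What remains is questioning plus systematic recording.

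**3. Illustrative size.** Inputs: true rate *p* of 14.2% to 16.1% in both groups (section 1.3), complete capture in AR patients (assumption), and a share *s* of events found by chart review (assumption; the documents give none).

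Apparent historical rate = *p* × *s*. Spurious excess = *p* × (1 − *s*). Ratio = 1/*s*.

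| *s* | Historical rate reads | Spurious excess (points) | Ratio |
|---|---|---|---|
| 0.5 | 7.1% to 8.1% | 7.1 to 8.1 | 2.00 |
| 0.7 | 9.9% to 11.3% | 4.3 to 4.8 | 1.43 |
| 0.9 | 12.8% to 14.5% | 1.4 to 1.6 | 1.11 |
| 1.0 | 14.2% to 16.1% | 0 | 1.00 |

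In patients: 10 × 0.014 = 0.14 events at the low end; 15 × 0.0805 = 1.2 events at the high end. One event moves the AR rate by 1/15 = 6.7 to 1/10 = 10 points.

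**4. What the sample can show.** Even with no complications in 15 AR patients, the one-sided exact probability is (1 − 0.161)^15 = 0.07 against 16.1% and (1 − 0.142)^15 = 0.10 against 14.2%. An improvement could not reach the 5% level against those rates even with identical ascertainment.

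**5. Features that could act the other way.** Data are dropped when consent is withdrawn (section 6) or refused after emergency inclusion (10.3). Non-fatal progression is not reported as an adverse event (8.1.1.1). Investigators who expect no device-caused events assess them (8.1.1). The documents do not allow these to be netted against step 3.

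**The case against.** **The link is inferred.** Section 8.1 compares clinical outcome data, and section 5.1 uses that phrase for Kakarla accuracy. No sentence says that counts from the adverse event pages will be set against institutional chart counts. This stands as a caution. The inference is still reasonable, because 4.2 equates recorded adverse events with complications and 5.1 asks for an improved complication rate.

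**Questioning hardly affects the main events.** The 14.2% to 16.1% range covers drain infection, haemorrhage and malplacement, which are found mostly by imaging or laboratory work. Many of these patients cannot answer in the acute phase: 4.2 gives GCS of 8 or less as an example, and 4.1.2 has patients sedated. This largely stands and confines the effect mainly to minor events. It does not remove it, because the AR numerator is not limited to those three types and recovering patients can be asked by follow-up.

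**The starting rate may itself come from records.** The title of one of the two sources cited for the range refers to an electronic health record repository. Discounting that rate again for chart under-capture is then doubtful. This stands, and it is why the table above is an illustration and not an estimate.

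**The sample is the larger limit.** With 2 events in 15, the exact 95% interval runs from roughly 2% to 40%, and no test is planned. This stands too, but it does not justify comparing differently collected rates when the remedy is cheap.

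**Stronger readings.** A reader might infer that the comparison is biased against AR overall, or that AR patients are examined more closely. The documents support neither: features working in the opposite direction are present, and evaluations and follow-up are stated to be standard care.

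**Conclusion.** The point holds in limited form. Ascertainment of complications differs between the two cohorts, and nothing in the plan harmonises it. Taken alone, this would tend to inflate the AR rate, mainly through minor events; the net direction cannot be determined.

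The documents give no size. A reader might take a gap of about 3 to 6 points as established. That figure follows only if chart review finds 60% to 80% of events at a true rate of 16.1% (0.161 × 0.2 = 3.2 points; 0.161 × 0.4 = 6.4 points), or about 0.3 to 1.0 events in 10 to 15 patients. The 60% to 80% is an assumption with no support in the documents.

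The consequence is confined to a descriptive secondary comparison. The primary accuracy endpoint and the safety reporting itself are not affected. The change should be made because it is cheap and is valid whichever way the net bias runs.

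**What to change.** Add to section 5.4 that the comparison of complication rate with institutional values uses one fixed list of objectively documented events, for example haemorrhage on a CT report, treated drain infection, and drain revision or re-operation. Both cohorts use the same definitions, time window, source and abstraction form. Report all other adverse events separately and without comparison, including those found only by trial questioning or recorded only because of the trial.

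The fixed list has to be the core of the change. Section 7.1 requires source documents to match the eCRF, so events prompted by the trial may already be in an AR patient's chart. Re-abstracting that chart without a restricted list might not remove the difference.

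The cost is a small extra abstraction for 10 to 15 patients. The compared rate will be lower than the full adverse event rate, so both must be shown and labelled. The change does not address the small sample, so the result remains descriptive.
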